2.3.3 Rationale for Targeting Children with Brainstem Gliomas

We and others have shown that PARP is highly expressed in pediatric GBMs and brainstem gliomas. As radiation treatment only leads to a transient response in these aggressive tumors, it is highly likely PARP over-expression, either at the time of diagnosis or in response to irradiation, contributes to apparent radiation resistance. We therefore propose to study the benefit of ABT-888, a PARP inhibitor, in overcoming the radiation resistance in pediatric DIPG.

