2.4.4.2 Selection of Brainstem Glioma

The proof-of-principle data described above suggests that urinary biomarkers may have potential to identify the presence of brain tumors. Further validation of this hypothesis would be bolstered by increasing the number of patients studied and following individual patients longitudinally to evaluate whether changes in disease status (response to therapy or progression) are reflected in corresponding changes in biomarker levels.

This project will focus on urinary biomarker levels in children with brainstem glioma. These patients represent a relatively homogenous population, minimizing variability in age (children), tumor pathology (high grade glioma), location (pontine, without concern for dissemination within the neuraxis) and treatment regimens. As these lesions are not treated with surgical excision, the imprecision inherent to measuring the degree of resection will not be present. The near-uniform progression of these tumors within a short window of time (>80% of patients manifest disease progression within 1 year) allows for data to be collected within a manageable time frame. In combination, these characteristics support the use of this group as an ideal study population.

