9.1.4 Urine Biomarkers

Participation in the urine biomarker study is strongly encouraged but optional.

9.1.4.1 *Sampling Strategy*

Urine will be collected at time of enrollment (pre-treatment), post ABT-888 plus radiation then at the time of each scheduled MRI. Urine will be collected throughout the time that each patient is receiving protocol treatment until disease progression.

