11.1.4 Progressive Disease (PD)

Progressive Disease (PD): Progressive neurologic abnormalities or worsening neurologic status not explained by causes unrelated to tumor progression (e.g., anticonvulsant or corticosteroid toxicity, electrolyte disturbances, sepsis, hyperglycemia, etc.), OR a greater than 25% increase in the bi-dimensional measurement, taking as a reference the smallest disease measurement recorded since the start of protocol therapy, OR the appearance of a new lesion, OR increasing doses of corticosteroids required to maintain stable neurological status or imaging.

* Consideration for possible pseudo-progression

For patients showing possible radiographic evidence of tumor progression on MRI during the first 6 months after initiation of ABT-888 and radiation (on required MRI studies performed at week 10, week 18, or 26), the treating physician will have the option of allowing the patient to remain on study, continuing protocol therapy, and repeating disease reassessment in 4-6 weeks. Provided that the patient does not show clinical deterioration consistent with tumor progression, has been on a stable or declining dose of steroids, and the subsequent MRI demonstrates tumor regression or stable disease, then the patient will remain on study and continue protocol therapy, and the frequency of subsequent MRI will revert to pre-specified intervals. If the repeat MRI after 4-6 weeks shows disease progression, rather than pseudo-progression, then the time of progression will be the date of the initial MRI, not the follow up scan. The addition of steroids is allowed, at the time of suspected pseudo-progression, as long as the patient can be maintained on a decreasing dose.

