13.4.3 Urine Biomarkers

Comparison of Urine Biomarker Levels in Patients vs. Controls:

In order to determine whether the levels of these urinary biomarkers are elevated in DIPG patients, we will compare median levels for tumor patients to levels in healthy age- and gendermatched controls using the Mann-Whitney U-test. Despite the presence of matched controls, Mann-Whitney U-test allows us to utilize a conservative approach compared to the Wilcoxon signed-rank test since matching by age and gender is done to reduce variability rather than to facilitate the use of methods for paired data. In addition, the percentage of patients and controls above the previously established cut-off values for each urinary biomarker will be compared using the chi-square test. Based on a preliminary power analysis for this chi-square test a sample

size of 58 brain tumor patients and 58 controls will provide 80% power with a conservative twosided alpha level of 0.01 in capturing a difference of 30% between the groups with respect to each urinary biomarker. We will also utilize ROC analysis for each biomarker in exploring various cut-points for differentiating between the control subjects and DIPG patients. Multivariable logistic regression models coupled with ROC analyses will be used to select a combination of these biomarkers in an attempt to improve their collective performance as a classifier.

Longitudinal Assessment of Changes in Biomarker Values and Their Association with Outcome: Using the data for patients who progress, for each biomarker we will compare the levels at baseline with levels at progression as determined by MRI to assess whether the biomarker values change and if so by how much. This will be done via Wilcoxon signed rank test and exact confidence interval estimates of the percent change. We will also tabulate the percentage of patients who have biomarker levels above the previously established cut points for each biomarker at baseline and at the time of progression. We will investigate whether the percentage of patients who are above/below the cutpoints for each of the biomarkers is different between baseline and time of progression via the McNemar's test. Provided adequate number of responses is present to make such analyses meaningful, we will also perform similar analyses comparing biomarker levels at baseline and at the time of response.

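### The paired urine-marker analyses compare progression only with the pre-treatment baseline, while size progression is judged from the smallest tumour measurement, so they cannot by themselves show whether a marker moves when disease progresses

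*Combined protocol and SAP*

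**What the plan says.** Section 2.4.4.2 gives the purpose of following patients over time: to "evaluate whether changes in disease status (response to therapy or progression) are reflected in corresponding changes in biomarker levels". Secondary objective 8 in section 1.3 likewise speaks of tracking changes in tumour status.

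For patients who progress, section 13.4.3 says "we will compare the levels at baseline with levels at progression as determined by MRI to assess whether the biomarker values change", and by how much. "This will be done via Wilcoxon signed rank test and exact confidence interval estimates of the percent change". It also tests whether the share of patients above or below each cut point "is different between baseline and time of progression via the McNemar's test". If there are enough responses, similar analyses compare baseline with the time of response. If there are enough events, a Cox model takes the eight markers as time-dependent predictors of PFS and OS.

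Section 9.1.4 sets the sampling: "Urine will be collected at time of enrollment (pre-treatment), post ABT-888 plus radiation then at the time of each scheduled MRI". The baseline sample is therefore taken before any treatment.

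Section 11.1.4 sets the size criterion for progression: "greater than 25% increase in the bi-dimensional measurement, taking as a reference the smallest disease measurement recorded since the start of protocol therapy". A new lesion, neurological worsening or an increasing steroid requirement also counts as progression. Section 2.3.3 states that "radiation treatment only leads to a transient response in these aggressive tumors".

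**The concern.** The MRI event and the urine contrast meant to reflect it use different reference points. MRI size progression is measured from the nadir, the urine change from diagnosis. The protocol expects radiation to produce a response first, so in responding patients the two references separate.

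Baseline and progression are both times of active disease. The null hypothesis that the paired tests examine is that the marker at progression equals the marker at diagnosis. The question in sections 1.3 and 2.4.4.2 is whether the marker moves when the disease progresses. No planned paired analysis runs from nadir to progression; the baseline-to-response comparison stops before progression.

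At stake is the reading of the longitudinal urine result. A useful marker could be reported as unchanged, or lower, at progression. That result would be driven by how far radiation had shrunk the tumour, not by a failure of the marker to follow it.

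**Working it through.** **The plan's own figure.** No effect size, power or significance level is stated for the baseline-to-progression tests, so there is nothing to reproduce for them. The only sizing figure in 13.4.3 (58 patients and 58 controls, 80% power, two-sided alpha 0.01, a 30-point difference) belongs to the patient-control chi-square test. It reproduces if the proportions are assumed to be 20% and 50%: n = [2.576√(2 × 0.35 × 0.65) + 0.842√(0.2 × 0.8 + 0.5 × 0.5)]² / 0.30² = 57.6, so 58 per group. The base rates are not stated, and the figure does not bear on this point.

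**Arithmetic from the protocol's definitions.** Let s be the fractional shrinkage from baseline to the smallest measurement (section 2.3.3 expects a transient response but gives no size), and g the growth from that measurement at progression (section 11.1.4: more than 0.25). Then:

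- size at progression ÷ size at baseline = (1 − s)(1 + g)
- size at progression ÷ size at nadir = 1 + g
- tumour back at baseline size when s = g / (1 + g); at g = 0.25 this is 0.25 / 1.25 = 20%

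| Shrinkage s | Progression ÷ baseline at g = 0.25 | Progression ÷ nadir | Regrowth needed to regain baseline, 1/(1 − s) − 1 |
|---|---|---|---|
| 0% | 1.25 | 1.25 | 0% |
| 10% | 1.125 | 1.25 | 11% |
| 20% | 1.00 | 1.25 | 25% |
| 30% | 0.875 | 1.25 | 43% |
| 40% | 0.75 | 1.25 | 67% |
| 50% (the PR threshold, 11.1.2) | 0.625 | 1.25 | 100% |

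The sign of the change does not need exact proportionality. Apart from assay noise, any marker that increases with tumour size is below its baseline value exactly when the tumour is.

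**Effect on the signed-rank test.** The documents do not give shrinkage, regrowth, marker noise or the number of pairs, so the following are assumptions: marker proportional to tumour size; log-scale noise SD 0.5 per sample; shrinkage SD 15 points (zero in the no-shrinkage case); regrowth of 25% plus an exponentially distributed excess; 30 pairs; two-sided 5%. Simulated power, as baseline reference v nadir reference:

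| Mean shrinkage | Mean excess regrowth 25 points | Mean excess regrowth 100 points |
|---|---|---|
| 0% | about 80% v 81% | both nearly 100% |
| 15% | about 30% v 80% | about 93% v nearly 100% |
| 30% | about 5% v 81% | about 59% v nearly 100% |
| 40% | about 17% v 80% | about 20% v nearly 100% |

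In the 40% row with 25 points of excess, almost all the significant baseline results are falls. At 30% shrinkage and 25 points, lower noise does not help the baseline contrast (log-SD 0.3: about 5% v 99%), nor do more patients (40 pairs at log-SD 0.5: about 5% v 91%), because the expected change from baseline is then close to zero.

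**The case against.** **The text says change, not rise.** A reader might infer that the plan tests whether markers rise at progression and would declare failure otherwise. The wording does not support that: it asks whether values change and by how much, so a fall would be reported with its size. This stands. What remains is that a fall from diagnosis would still say nothing about movement from nadir.

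**Serial values are used elsewhere.** A reader might infer that the plan ignores the on-treatment samples. It does not: the time-dependent Cox model uses them, and section 2.4.4.2 expects more than 80% of patients to progress within a year, so events may well suffice. This narrows the gap. However, the model is conditional, and it relates marker level to the hazard of PFS and OS events without estimating within-patient change from nadir.

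**The marker need not follow size.** Section 2.4.4 describes markers of vascular stability and metabolic activity that complement imaging. If a marker reflects activity and not area, the size ratios do not carry over. This limits the magnitude, but it does not make baseline the matching reference for progression.

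**The 5% figure is one scenario.** The 25% growth is a floor, and scheduled scans are roughly eight weeks or more apart, so regrowth at detection may be larger. With a mean excess of 100 points the baseline contrast keeps about 59% power at 30% shrinkage. Without shrinkage nothing is lost, and progression by a new lesion was not modelled. All of this stands.

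**The nadir reference has its own weaknesses.** The week-10 sample follows six to seven weeks of ABT-888 and radiation, so a later rise could be recovery from a direct treatment effect on the marker. In near-stable tumours, measurement error may decide which scan is smallest. Both stand as limitations to state.

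**Conclusion.** The point holds, at minor severity. The mismatch of references is in the text, and the break-even at 20% shrinkage follows from the 25% rule alone. Beyond that, if progression is called near the threshold, a marker that follows tumour size shows no change or a fall from baseline. The planned paired contrast alone therefore cannot answer the progression-tracking question.

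How much power is lost is not known. It rests on assumed shrinkage, regrowth, noise, number of pairs and a size-proportional marker. For 30 pairs, log-SD 0.5 and 30% mean shrinkage, baseline-referenced power is about 5% to 59% as mean excess regrowth goes from 25 to 100 points, against about 81% to nearly 100% with the nadir reference. Across the scenarios examined, the nadir reference was never materially worse.

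A reader might go further and infer that the urine study cannot detect progression, or that the trial's conclusions are at risk. The documents support neither. The Cox model uses the serial levels, participation is optional, the objective is exploratory and listed last among the secondary objectives, and no efficacy, safety or stopping decision depends on it.

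**What to change.** In section 13.4.3, add a paired signed-rank, percent-change and McNemar comparison of the progression sample with the urine sample taken at the smallest-measurement MRI before progression, and name it as the analysis that answers the progression-tracking question. Specify that:

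- the reference sample is chosen by the scan, never by the marker value, since picking the lowest marker would create a rise through regression to the mean;
- baseline is the reference when baseline is the smallest measurement;
- baseline v progression is still reported, as a comparison with diagnosis.

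The cost is a few sentences. The samples are already scheduled under section 9.1.4, and no clinical procedure changes. Three limitations should be stated alongside: patients who progress at the first post-radiation scan have only the baseline reference; the week-10 sample may carry a direct treatment effect on the marker; and in near-stable tumours the nadir scan may be set by measurement error.

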2.4.4.1 Preliminary data

We reported the first demonstration of the utility of urinary biomarkers in brain tumors, including the use of molecules specifically related to the regulation of vascular stability⁴³ and recently published a proof-of-principle case series, that specifically evaluated the ability of a panel of urinary biomarkers such as MMP-2, MMP-9, NGAL and VEGF (See Figure 4 and **Table 6** and **Table 7**).⁴⁴ The results of this series support the premise that levels of urinary biomarkers can not only predict the presence of brain tumors but also that they change in response to effective surgical therapy (see Figure 5).

We have subsequently identified additional biomarkers that can be detected in urine in association with pediatric brain tumors. These new markers (HB-EGF, EGF, HGF and TIE-2) allow for greater sensitivity in identifying the presence of disease. Specific to this project, these markers have been evaluated in pediatric patients with various subtypes of high grade glioma, including both GBM and anaplastic astrocytoma.

Table 6								
Demographics, MMP's and VEGF for Brain Tumor Patients and Controls								
Variable	Contro	ol Group ((n=23)	Brain T	`umor Group	o (n=28)	Р	
	Median	IQR	Range	Median	IQR	Range		
Age, yr	22	4-55	0-71	32	8-58	1-73	0.37	
MMP-9	0	0-0	0-6	0.6	0-5.7	0-294	< 0.001*	
MMP-9/NGAL	0	0-0	0-12.8	0.8	0.2-1.0	0-1.1	< 0.001*	
MMP-2	0	0-0	0-3	4.3	0.8-8.8	0-27	< 0.001*	
VEGF	25	0-250	0-391	753	451-957	25-4462	< 0.001*	
Female sex, no. (%)	11(48)				13 (46)		0.92	

T 11 (

Table '	7
---------	---

Results of Receiver Operating Characteristic (ROC) Curve Analysis and Diagnostic Performance Indices of MMP-2 and VEGF							
	01 NIN	P-2 and VEGF					
Biomarker	AUC	95% CI	P value				
MMP-2 (ng/ml)	0.894	0.800-0.987	< 0.0001				
VEGF (pg/L)	0.965	0.913-0.999	<0.0001				
Cutoff Points	Sensitivity (95% CI)	Specificity (95% CI)	Accuracy (95% CI)				
MMP-2 >0.4 ng/ml	82.1 (65.2-94.0)	95.7 (78.1-99.9)	88.2 (76.1-95.6)				
VEGF >350 pg/L	95.2 (76.2-99.9)	89.5 (66.9-98.8)	92.5 (80.0-98.5)				

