9.1.4.5 Description of Urine Biomarker Assay

All samples will be analyzed for the presence or absence of each of the 8 biomarkers. Zymography will be performed to analyze for MMP-2, MMP-9 and MMP-9/NGAL in a blinded fashion by the laboratory examiner and recorded as a positive or negative result, following a protocol well-established in our laboratory which has been validated in the literature.39

Zymography

Samples will be frozen immediately after collection and stored frozen (-20C) until assay. Aliquots of each sample will be centrifuged at 4,000 rpm for 5 min at 4C and the supernatants collected. Urine samples (30 uL) will be mixed with buffer consisting of 4% SDS, 0.15 mol/L Tris (pH 6.8), 20% (v/v) glycerol, and 0.5% (w/v) brom-phenol blue. Samples will be applied, without boiling, into wells of a 4% acrylamide Laemmli stacking gel/10% SDS-acrylamide separating gel containing 0.1% (w/v) gelatin (Life Technologies, Inc.) on a mini gel apparatus. Gels will be run at 15 mA/gel during stacking and at 20 mA/gel during the resolving phase at room temperature. After electrophoresis, the gels will be soaked in 2.5% Triton X-100 with gentle shaking for 30 min at ambient temperature with one change of detergent solution. The gels will then be rinsed and incubated overnight at 37°C in substrate buffer [50 mmol/L Tris-HCI buffer (pH 8), 5 mmol/L CaCl2, and 0.02% NaN3,]. After incubation, gels will be stained for 15 to 30 min in 0.5% Coomassie Blue R-250 in acetic acid, isopropyl alcohol, and water (1:3:6); destained in acetic acid, ethanol, and water (1:3:6), and photographed. The presence or absence of each species (MMP-2, MMP-9, MMP-9/NGAL) will be recorded and relative intensities (if present) noted.

ELISA

ELISA will be used to establish quantitative levels of each of the 8 biomarkers. Kits will be obtained from the manufacturers (R&D systems and Bioplex/Bio-Rad). Specimens, standards and reagents will be prepared according to manufacturer's instructions. Protein concentration will be determined via the Bradford method using bovine serum albumin as the standard. Results will be recorded as ng/ml or pg/L.

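### The only estimate of how much a urine marker changes is percent change, which has no value at a zero baseline; the plan's preliminary MMP-9 data suggest that may be a quarter or more of patients

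*Combined protocol and SAP*

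**What the plan says.** Section 13.4.3, in the longitudinal part, takes the patients who progress and states that "for each biomarker we will compare the levels at baseline with levels at progression as determined by MRI", in order to learn whether values change and by how much. The method follows: "This will be done via Wilcoxon signed rank test and exact confidence interval estimates of the percent change". The same approach is to be used for baseline against response if there are enough responses. The section also tabulates patients above the cut points at both times and applies McNemar's test. Percent change is the only measure of the size of the change.

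Section 9.1.4.5 describes two assays. For the first, "ELISA will be used to establish quantitative levels of each of the 8 biomarkers". For zymography, "The presence or absence of each species (MMP-2, MMP-9, MMP-9/NGAL) will be recorded and relative intensities (if present) noted", so an absent marker is an expected result. Neither section says what to do with a zero or undetectable value. Nor do they say whether percent change is per patient or of a group summary, or whether the interval is for a median, a Hodges-Lehmann estimate or a mean.

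Table 6 in section 2.4.4.1 ("Demographics, MMP's and VEGF for Brain Tumor Patients and Controls") gives median, interquartile range and range in the tumour group:

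- MMP-9: 0.6, 0-5.7, 0-294
- MMP-9/NGAL: "0.8 0.2-1.0 0-1.1"
- MMP-2: "4.3 0.8-8.8 0-27"
- VEGF: "753 451-957 25-4462"

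**The concern.** A patient whose baseline is zero has no percent change. Such a patient can only stay at zero or rise, so exclusion is selective: it takes out rises and never falls. A marker that goes from undetectable to detectable at progression is the kind of signal this part of the study looks for, and those patients would be missing from the only estimate of its size. Patients going the other way stay in, at -100%.

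At stake is the reported size of the MMP-9 change. Without a zero rule and a named estimator, the figure would depend on choices made after the data are seen.

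**Working it through.** **No planned figure to reproduce.** The section's only sample size, 58 patients and 58 controls, belongs to the patient-versus-control chi-square test. It reproduces if the unstated base rates are 50% and 80% (power 80.4% at two-sided alpha 0.01), but it has no bearing on percent change.

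**Step 1: how many zeros.** Per-patient percent change is 100 x (Y - X)/X, with X the baseline and Y the later value; it is undefined at X = 0. A lower quartile of 0 among 28 patients means at least 28 x 0.25 = 7 zeros for MMP-9 (8 under interpolating quartile rules). For MMP-2 and MMP-9/NGAL the minimum is 0 but the lower quartiles are 0.8 and 0.2, so zeros occur in fewer than about a quarter. The VEGF minimum is 25, so there are none. Table 6 does not cover the other four markers.

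**Step 2: the selection, without a distributional model.** Let p be the share at zero at each visit and c the share going from zero to positive. With no true change, the same share c goes from positive to zero. Patients kept number 1 - p. Of these, c fall to zero, and the remaining 1 - p - c split evenly between rises and falls. The share of kept patients who rise is therefore (1 - p - c)/2 divided by (1 - p):

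- p = 0.25, c = 0.08: (0.67/2)/0.75 = 0.335/0.75 = 45%
- p = 0.40, c = 0.16: (0.44/2)/0.60 = 0.22/0.60 = 37%

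Fewer than half rise although nothing has changed, so the median must be negative. The values of c come from the simulation in step 3.

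**Step 3: size, by simulation.** Assumptions: zero-inflated lognormal matched to the MMP-9 median 0.6 and upper quartile 5.7; share of zeros 25% or 40%; Gaussian-copula correlation between visits 0.5 or 0.8; no true change; 400,000 pairs. The zero shares above 25% and the correlations are not in the documents. With 25% zeros, 0.6 and 5.7 sit at one third and two thirds of the positive part (z = -0.431 and +0.431), so the log-SD is ln(5.7/0.6)/0.862 = 2.251/0.862 = 2.61.

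| Zeros | Correlation | Median % change, kept patients | Mean % change, kept patients |
|---|---|---|---|
| 25% | 0.8 | -26% | +1,242% |
| 25% | 0.5 | -55% | +10,370% |
| 40% | 0.8 | -34% | +324% |
| 40% | 0.5 | -66% | +1,078% |

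The mean is unstable: repeat runs put the largest value as high as about +12,800%. The Hodges-Lehmann estimate of percent change, in samples of 58, ran from about -10% to +69%. Between 8% and 16% of patients went from zero to positive (all excluded), and an equal share went from positive to zero (all counted). The Hodges-Lehmann paired difference on all pairs was 0.0 in every scenario.

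**Step 4: a second model.** Lognormal levels with median 0.6, values below the 25th percentile set to zero, log-SD 1.0 to 3.34, correlation 0.5 to 0.9, 58 patients. With no true change the median in kept patients was -4% to -49%, and the Hodges-Lehmann percent change -8% to +55%. With a true doubling (+100%), the median read +2% to +91% and the Hodges-Lehmann estimate +92% to +207%. Against the same estimator on everyone's uncensored levels, dropping the zeros lowered both estimators in every scenario, but the result did not always lie below the true change.

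**The case against.** The strongest reply is that the plan does not rest on this interval. A signed-rank test on absolute differences keeps patients with a zero baseline, and McNemar's test is defined at zero and counts crossings in both directions. That stands: zero-to-positive patients leave the percent-change interval, not the whole analysis. It does not supply a size of change, however, and a cut point need not be zero. Table 7 prints cut points for MMP-2 and VEGF only.

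A second reply is that Table 6 is not this population. It is an earlier brain tumour series with median age 32 and range 1-73. This also stands; the quarter is an assumption when carried to children with DIPG, and a printed 0 could be a small value rounded down. Percent change would still be unstable with a denominator close to zero.

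Third, percent change could mean the change in a group summary, which is defined when the median is 0.6. The text does not say so, and that reading needs a different interval from the one a per-patient change would use.

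A reader might infer more than the documents support:

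- *That the estimate is biased downward, or shows a fall when nothing has changed.* This is true of the median. It is not general: the mean comes out strongly positive and the Hodges-Lehmann percent change can have either sign. The plan names none of them.
- *That 14 or 15 of 58 patients are lost.* The 58 belongs to another analysis. The longitudinal set is patients who progress with paired urine, and urine collection is optional (section 9.1.4).
- *That the test and the interval will point in opposite directions.* They may use different patients, but opposite conclusions were not shown.

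**Conclusion.** The point holds in limited form. Section 13.4.3 states one rule for the size of a marker change, and that rule gives no value at a zero baseline. For MMP-9, Table 6 suggests a quarter or more of patients may be affected, provided the share carries over to DIPG; for MMP-2 and MMP-9/NGAL it is fewer, and for VEGF none on these data. In the remaining patients the estimate is distorted, with size and direction set by an unnamed estimator: under no change and the step 3 assumptions, the median is about -26% to -66% and the mean strongly positive. The milder second model starts at -4% for the median, so the existence of the distortion is firmer than its size.

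This touches one exploratory objective (section 1.3, item 8) with optional participation. No dose, stopping rule or primary conclusion depends on it. It should be corrected because a better-defined quantity is available at almost no cost.

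**What to change.** In section 13.4.3, for both the progression and the response comparisons, replace the percent-change interval with the Hodges-Lehmann paired difference and the confidence interval that inverts the signed-rank test. Use all pairs, including those with zeros. State how tied zero differences (zero at both visits) are treated, because with such ties the interval is not straightforwardly exact.

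For the MMP markers, also report the numbers of patients going from zero to positive and from positive to zero.

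If percent change or a log ratio is kept, restrict it to markers without zeros, such as VEGF, or prespecify a non-detect rule and name the estimator. The documents give no assay limit, so a substitution rule would have to state one. With many non-detects the result would depend on the value chosen.

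The cost is analysis wording only, with no added samples or visits. The small downside is a result in concentration units rather than a percent, which is harder to compare across markers.
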